4.6.2 Data Collection and Follow-up for Withdrawn Subjects

Should a subject request to withdraw or be withdrawn from the study by the PI, the subject's reason for withdrawal will be documented.

5 Study Product

5.1 Description and Treatment Regimen

An outline of the study timepoints is provided in Table 5.1-1. At Screening, subject eligibility will be determined using an online survey (**Appendix A**). Participants will be enrolled in the study in groups of 10 at a time. Participants will eat a meal the night before the study and begin the study the next morning in a fasted state (*i.e.*, overnight, 12-hr fast). The time at which the last meal was consumed and the study start time should be recorded using the online portal (**Appendix C**).

The study will be approximately 300 minutes (5 hours), from start to finish. Completion of study questionnaires, assessment of blood BHB levels, and consumption of the Avela™ beverage will be completed, as per Table 5.1-1; a detailed description of the methodology for each study timepoint is provided in section 6.0 of this clinical study protocol.

Table 5.1-1 Clinical Study Outline

Assessment	Tool Utilized	Screening (up to 7 days prior to test day)	Time (min)								
			0	30	60	90	120	180	240	300	
Eligibility for study participation	On-line Survey	X	-	-	-	-	-	-	-	-	-
GI symptomatology	mVAS GI Symptoms Tool	-	X	X	X	X	X	X	X	X	X
Sleepiness/Alertness Assessment	Stanford Sleepiness Scale	-	X	X	X	X	X	X	X	X	X
Blood BHB levels	Keto-Mojo Monitor	-	X	X	X	X	X	X	X	X	X
(R)-1,3-butanediol consumption	Avela™	-	X	X	X	-	-	-	-	-	-
ALOHA Bar consumption	Not applicable	-	-	-	-	-	-	-	X	-	-

BHB = beta-hydroxybutyrate; GI = gastrointestinal; min = minutes; mVAS = modified visual analogue scale.

5.2 Method for Assigning Subjects to Treatment Groups

All subjects included in the study will be assigned to receive the active investigational product [Avela™ (R)-1,3-butanediol] (*i.e.*, there is only one group for the study, with a before, after study design). Upon enrolment, each participant will be provided with a unique identification number.

5.3 Subject Compliance Monitoring

Compliance of subjects will be assessed by using compliance records. Participants must consume all 3 doses of product, at the specified timepoints, to meet compliance requirements.

5.4 Prior and Concomitant Therapy

Subjects may continue their use of medications and/or dietary supplements throughout the study period, so long as they do not have conditions or are taking medications are not contra-indicated (see Exclusion Criteria in Section 4.4).

5.5 Handling of Study Product

5.5.1 Dispensing of Study Product

At screening, all subjects included in the study will be provided with the following:

- 3 x 4 oz (118 mL) bottles of water premixed with Avela™ [each providing 11.5 g of (R)-1,3-butanediol];
- Lancets;
- Alcohol swabs;
- 1 sharps container;
- 1 shot glass with the Avela™ logo;
- 1 Keto Mojo BHB monitor and ketone test strip;
- Bandages;
- 1 pregnancy test [if applicable];

- 1 x measuring tape;
- 1 x ALOHA Organic Plant Based Protein Bar (Caramel Sea Salt);
- 1 duffel bag;
- 1 x study consent form; and
- 1 x study instruction sheet (**Appendix B**).

5.5.2 Return or Destruction of Study Product

The PI will maintain records of the product's delivery to the study participants and its use by each subject. These records should include dates, quantities, batch/serial numbers, expiration dates (if applicable), and the unique code numbers assigned to the trial subjects. Investigators should maintain records that document adequately the doses provided to subjects and consumed by subjects so as to permit complete reconciliation of all investigational product(s). As the study product is a lawful food ingredient in the United States (U.S.), there will be no requirement for study participants to return unused study product to Genomatica. Rather, any unused study product can be disposed of by the participant by flushing down the toilet or pouring down the drain. The sharps container is provided with a prepaid outer shipping carton and water-resistant sealing tape and a shipping manifest form for tracking and certificate of destruction. Study subjects will follow the mailing instructions provided with the sharps container to return the container.

6 Study Schedule

A tabular summary of the schedule of procedures is provided in Table 5.1-1. An overall review of the order of events on the test day is provided in Table 6-1. A breakdown of the order of events at each study timepoint (*i.e.*, prior to study start and at 0, 30, 60, 90, 120, 180, 240, and 300 minutes) is provided in Sections 6.2.1 to 6.3.0.

Table 6-1 Order of Events on Study Test Day

Timepoint (min)	mVAS GI Symptoms Tool	SSS	BHB Measure	Consumption of Avela™	Consumption of ALOHA Bar
0	1	2	3	4	-
30	1	2	3	4	-
60	1	2	3	4	-
90	1	2	3	-	-
120	1	2	3	-	-
180	1	2	3	-	-
240	1	2	3	-	4
300	1	2	3	-	-

6.1 Screening – Day 1 (Investigative Staff)

- Assess participant eligibility using responses to online survey (**Appendix A**).
- If participant is eligible, obtain signature of subject on study Informed Consent Form for study participation.
- Provide participants with three 4 oz (118 mL) bottles of water premixed with Avela™ [each providing 11.5 g of (R)-1,3-butanediol]; lancets; alcohol swabs; 1 Keto Mojo BHB monitor; bandages; measuring tape; pregnancy test [if applicable]; one ALOHA Bar; 1 x study consent form; and 1 x study instruction sheet (**Appendix B**).

6.2 Study Test Day – Day 2 (Study Participant)

6.2.1 Prior to Study Start

- **Pregnancy test [if applicable]**
 - If a participant answered “no” to both of the study screening questions:
 - “If you are a female, are you post-menopausal, defined as not having had a period for 12 consecutive months or longer?”
 - “If you are a female, have you had any procedure that would result in you not being able to have children, such as “tying of tubes” or a removal of your ovaries?”
 - Then the subject is to take the pregnancy test prior to study start and proceed only if the test is negative (the result of the test will be included on the online portal).
- **Setting up the Keto-Mojo Monitor**
 - The subject will be instructed to download the MyMojoHealth app from the Apple Store or Google Play.
 - The subject will sync the app with his/her Keto-Mojo Monitor.
 - The study coordinator will send the subject a request, on his/her App, to join the study account, in order to share all BHB readings acquired during the study. Each subject’s data will be downloaded *via* the account.
- The subject will familiarize themselves with the online system for data recording.

6.2.2 0 min timepoint

- Using the online portal, the subject will:
 - Record the time their last meal was consumed.
 - Record the start time of the study.
 - Complete the mVAS GI symptoms tool.
 - Complete the SSS.

- Measure their blood BHB level using the Keto Mojo Monitor and record the value on the online portal.
- Start their on-screen timer.
- Consume one (1) bottle of premixed Avela™ liquid within a 5-minute time period.

6.2.3 30 min timepoint

- Using the online portal, the subject will:
 - Complete the mVAS GI symptoms tool.
 - Complete the SSS.
- Measure their blood BHB level using the Keto Mojo Monitor and record the value on the online portal.
- Consume one (1) bottle of premixed Avela™ liquid within a 5-minute time period.

6.2.4 60 min timepoint

- Using the online portal, the subject will:
 - Complete the mVAS GI symptoms tool.
 - Complete the SSS.
- Measure their blood BHB level using the Keto Mojo Monitor and record the value on the online portal.
- Consume one (1) bottle of premixed Avela™ liquid within a 5-minute time period.

6.2.5 90 min timepoint

- Using the online portal, the subject will:
 - Complete the mVAS GI symptoms tool.
 - Complete the SSS.
- Measure their blood BHB level using the Keto Mojo Monitor and record the value on the online portal.

6.2.6 120 min timepoint

- Using the online portal, the subject will:
 - Complete the mVAS GI symptoms tool.
 - Complete the SSS.
- Measure their blood BHB level using the Keto Mojo Monitor and record the value on the online portal.

6.2.7 180 min timepoint

- Using the online portal, the subject will:
 - Complete the mVAS GI symptoms tool.
 - Complete the SSS.
- Measure their blood BHB level using the Keto Mojo Monitor and record the value on the online portal.

6.2.8 240 min timepoint

- Using the online portal, the subject will:
 - Complete the mVAS GI symptoms tool.
 - Complete the SSS.
- Measure their blood BHB level using the Keto Mojo Monitor and record the value on the online portal.
- Consume the provided ALOHA Bar within 7 minutes.

6.2.9 300 min timepoint

- Using the online portal, the subject will:

- Complete the mVAS GI symptoms tool.
- Complete the SSS.
- Measure their blood BHB level using the Keto Mojo Monitor and record the value on the online portal.

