4.2 Total Number of Subjects and Sites

The proposed clinical study is being conducted by Genomatica. Thirty Genomatica employees (males and females) are being recruited for the study. There is no sample size calculation, as there is no control group and the study is a pilot study, with the main objective of understanding ketone (BHB) levels following consumption of (R)-1,3-butanediol. 30 participants are to be included, due to the inherent

variability in the GI symptomology questionnaires. Of note, in other studies of food ingredients (e.g., inulin¹, sorbitol², erythritol + fructose³) where GI tolerance was an outcome of interest, sample sizes ranged from 26 to 37 participants

Genomatica employees who express interest in participating in the study and who meet the eligibility criteria for study inclusion will complete the study remotely, within their own homes, using equipment provided by Genomatica (i.e., lancets, sharps container, alcohol swabs, Keto Mojo BHB monitor and ketone test strips (and glucose test strips, not to be used in the study), bandages, pregnancy test [if applicable], measuring tape, three 4 oz. (118 mL) bottles of sealed water premixed with Avela™ [each providing 11.5 g of (*R*)-1,3-butanediol], 1 shot glass with the Avela™ logo, an ALOHA Organic Plant Based Protein Bar (Caramel Sea Salt), 1 duffel bag, 1 consent form, and study instructions. All study-related data will be entered and transmitted by each study participant using an electronic platform, using surveys that will protect the identity of each participant.

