4.6 Early Withdrawal of Subjects

4.6.1 When and How to Withdraw Subjects

Subjects may withdraw consent or be removed from the study by the Principal Investigator (PI). In the event that a subject is withdrawn from the study, the reason for the withdrawal will be documented, with the primary reason selected from the following standard categories:

- Withdrawal of consent: the subject requests to withdraw from further participation in the study in the absence of a medical need to withdraw as determined by the PI.
- Lost to follow-up: for unknown reasons, the subject did not upload their study results on to the electronic platform.
- Poor compliance: the subject consumes only 1 or 2 of the 3 servings of the study product; is found to meet an exclusionary criterion; and/or is not complying with other study obligations.
- AE: in the judgment of the PI and in the best interests of the subject, events that require discontinuation of study product (includes all categories of study product relatedness: None, Remote, Possible, Probable, or Highly Probable).
- Death: death of the subject.
- Other: causes of premature termination from the study other than the above, such as theft or loss of study products, termination of study by Sponsor, *etc.*

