7.3 Questionnaire Assessments

7.3.1 GI Symptoms Assessment

A validated tool to measure GI tolerability of (R)-1,3-butanediol will be utilized. The mVAS GI symptoms tool is a self-administered questionnaire, which is modelled after the validated “gold standard” measurement tool predominantly used to test clinical gastroenterology scenarios (Bengtsson *et al.*, 2013). Gaskell *et al.* (2019) tested the reliability of the mVAS in assessing GI symptoms during exercise, with and without dietary interventions. The mVAS has been modified slightly for this clinical study protocol, as there is no exercise employed in this study. The mVAS uses a 10-point rating scale to self-report on GI symptoms; 1–4 is indicative of mild GI symptoms (*i.e.*, sensation of GI symptoms, but not substantial enough to interfere normal activities); 5–9 is indicative of severe GI symptoms (*i.e.*, GI symptoms substantial enough to interfere with normal activities), and 10 is indicative of extremely severe GI symptoms warranting cessation of all other activities. If no specific GI symptom is reported, this would be recorded as a 0. A sample of the questionnaire is available within the screen captures of the online portal (**Appendix C**). In the study by Gaskell *et al.* (2019), GI symptoms, such as regurgitation and defecation, were rated dichotomously, either as 0 (no symptom) if they did not result in a cessation of exercise or as 10 (extremely severe symptoms) if they resulted in either a temporary or complete cessation of exercise; in this clinical study, these have been modified to a full 10-point VAS scale. All subjects will complete the mVAS at baseline (0 minutes), and at 30, 60, 90, 120, 180, 240, and 300 minutes.

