14. Use the Keto-Mojo monitor to measure your blood BHB level and record this value on the online portal.
15. **Consume one of the Avela™ beverages within 5 minutes.**

60 minutes

16. Using the online portal, complete the mVAS for GI symptoms, followed by the SSS.
17. Use the Keto-Mojo monitor to measure your blood BHB level and record this value on the online portal.
18. **Consume one of the Avela™ beverages within 5 minutes.**

90 minutes

19. Using the online portal, complete the mVAS for GI symptoms, followed by the SSS.
20. Use the Keto-Mojo monitor to measure your blood BHB level and record this value on the online portal.

120 minutes

21. Using the online portal, complete the mVAS for GI symptoms, followed by the SSS.
22. Use the Keto-Mojo monitor to measure your blood BHB level and record this value on the online portal.

180 minutes

23. Using the online portal, complete the mVAS for GI symptoms, followed by the SSS.
24. Use the Keto-Mojo monitor to measure your blood BHB level and record this value on the online portal.

240 minutes

25. Using the online portal, complete the mVAS for GI symptoms, followed by the SSS.
26. Use the Keto-Mojo monitor to measure your blood BHB level and record this value on the online portal.
27. Consume the ALOHA Bar that has been provided, within a 7-minute timeframe.

300 minutes

28. Using the online portal, complete the mVAS for GI symptoms, followed by the SSS.
29. Use the Keto-Mojo monitor to measure your blood BHB level and record this value on the online portal.

Congratulations! You have now completed the study! Please open the Keto-Mojo App to allow it to sync with the Keto-Mojo Monitor and mail back the sharps container using the prepaid outer shipping carton, when convenient.

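### Servings 2 and 3 are taken at home straight after the GI symptom score, and the visible text has no hold even at the top score of 10

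*Combined protocol and SAP*

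**What the plan says.** Section 4.2 has participants "complete the study remotely, within their own homes". Sections 6.2.3 (30 minutes) and 6.2.4 (60 minutes) give one sequence: mVAS, Stanford Sleepiness Scale, blood BHB, then the drink. The drinking step reads "Consume one (1) bottle of premixed Avela™ liquid within a 5-minute time period". Table 6-1 numbers these steps 1 to 4, and section 3.1 stresses keeping the order. The sheet that participants work from (Appendix B, steps 13 to 18) repeats the sequence and ends each block with "Consume one of the Avela™ beverages within 5 minutes". Section 5.3 counts a participant as compliant only if all three servings are taken on schedule.

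Section 7.3.1 grades the mVAS: 1 to 4 is mild, 5 to 9 is severe, and "10 is indicative of extremely severe GI symptoms warranting cessation of all other activities". It ties no dosing action to any grade.

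Three other provisions come near the point. Section 6.2.1 has a go/no-go step for the pregnancy test: the participant may "proceed only if the test is negative". Section 4.6.1 lists, as a withdrawal reason left to the investigator's judgment, "events that require discontinuation of study product". Section 9.2 recommends prompt treatment for any adverse event.

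**The concern.** A participant can enter the worst possible symptom score and find, a few lines later, an instruction to drink more of the product within 5 minutes. The visible text describes no staff present and no review of entries between servings, so the instruction sheet is the main visible safeguard at the moment of dosing. What is at stake is the participant's safety during a session of about five hours at home. A second effect is that the plan does not foresee how BHB would be reported for someone who took fewer than three servings.

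**Working it through.** The point rests on reading the provisions side by side. The plan states no figure for it, and the dose arithmetic only gives scale.

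**1. Does any visible provision act between the score and the next bottle?**

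| Provision | What it does | Acts before serving 2 or 3? |
|---|---|---|
| 6.2.3, 6.2.4, Table 6-1, Appendix B steps 13 to 18 | mVAS, sleepiness, BHB, drink | No condition attached |
| 7.3.1 | Defines 10 as a level at which to stop other activities | Implies stopping; gives no instruction about the next serving |
| 6.2.1 | Pregnancy-test gate | Acts once, before the start; not about symptoms |
| 4.6.1, adverse-event reason | Investigator judges that product must stop | No threshold, and no same-session review described |
| 4.6.1, withdrawal of consent | Participant may leave | Available, but not prompted by a score |
| 9.2 | Advises seeking treatment | Does not say to skip or delay the next serving |

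Servings are 30 minutes apart, and the drink follows the score within the same timepoint. Nothing listed tells the participant to hold the bottle.

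**2. Dose per kilogram.** Section 1.3 gives 0.16 to 0.49 g/kg for 11.5 to 34.5 g. Section 1.3 does not state the weight behind this, but 70 kg (the weight used for examples in 1.4) reproduces it: 11.5/70 = 0.16 and 34.5/70 = 0.49.

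The minimum eligible weight in 4.3 is 110 lb: 110 × 0.4536 = 49.9 kg.

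| Servings taken | Grams | Share of 34.5 g | g/kg at 70 kg | g/kg at 49.9 kg |
|---|---|---|---|---|
| 1 | 11.5 | 11.5/34.5 = 33% | 0.16 | 11.5/49.9 = 0.23 |
| 2 | 23.0 | 23.0/34.5 = 67% | 23.0/70 = 0.33 | 23.0/49.9 = 0.46 |
| 3 | 34.5 | 100% | 0.49 | 34.5/49.9 = 0.69 |

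Treating a hold as final, one at 30 minutes withholds 34.5 − 11.5 = 23.0 g. One at 60 minutes withholds 34.5 − 23.0 = 11.5 g.

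**3. What a hold leaves to measure.** After 30 minutes, assessments remain at 60, 90, 120, 180, 240 and 300 minutes (6 of 8). After 60 minutes, 5 of 8 remain. A held participant who feels able to go on still contributes data.

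**4. What the background section says about severe symptoms.** Section 1.4 reports nausea, euphoria and dizziness with single boluses of 0.5 and 0.7 g/kg. In the split-dose cycling study, one of nine participants had severe abdominal pain, and four retched, which the text attributes to taste. In the running study, which gave 0.5 g/kg in three divided doses, no adverse GI effects were reported. The cycling study used an (R,S) product, the chirality in the running study is unknown, and both main studies involved exercise. None of this yields a rate for the present regimen. It shows only that split dosing has not ruled out severe symptoms.

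**The case against.** The strongest reply is that the decisive page is missing. Scores are entered in the online portal, whose screens (Appendix C) are not shown, and section 12 says the consent form covers sickness caused by the research. A prompt could sit in either place. This stands, and it limits the claim to the visible text. It does not remove the point, because Appendix B, which participants follow step by step, is fully visible and has no hold.

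Second, the plan does foresee stopping. A 10 by definition calls for stopping other activities, 4.6.1 allows withdrawal, 9.2 advises treatment, and unused product may be discarded. This also stands: nothing forbids stopping. But the participant must set the general meaning of a score against an explicit dosing step and a three-serving compliance rule. A written hold removes that choice.

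Third, the pregnancy-test gate enforces an exclusion criterion, so it is a weak parallel. Agreed. It shows only that the plan can write a go/no-go step for participants to apply themselves.

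Fourth, the total is within the product's stated GRAS use, and divided dosing is itself the mitigation (1.3 and 1.5). That lowers the expected need for a hold but does not say what to do when one is needed.

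A reader might also infer that 4.6.1 would misfile a symptom-driven stop, because its poor-compliance reason includes the case where "the subject consumes only 1 or 2 of the 3 servings of the study product". The documents do not support that. The reason is chosen "with the primary reason selected from the following standard categories", the adverse-event reason is on that list for the investigator to select, and no planned endpoint depends on the withdrawal reason.

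**Conclusion.** The point holds as a gap in the visible instructions: servings 2 and 3 follow the symptom score with no symptom-based hold, even at 10. It concerns participant safety and is worth correcting because the correction costs so little.

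Its size is known per person and unknown in total. A hold would spare an affected participant 11.5 g or 23.0 g of the 34.5 g. The documents give no frequency of a 10 at 30 or 60 minutes, so no count of affected participants can be given.

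Two stronger readings are tempting. One is that the fixed dose will harm light participants, since 0.69 g/kg is close to the 0.7 g/kg bolus that caused symptoms. That bolus was taken at once, whereas 0.69 g/kg here is spread over about an hour and applies only at exactly 110 lb, so the comparison predicts no rate. The other is that the gap undermines the BHB result. It does not: section 9.2 requires adverse events to be recorded, section 5.5.2 asks for records of doses consumed, and scores already entered remain available.

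The conclusion assumes that no prompt exists in the portal or consent form. If one does, what remains is a matter of making the documents agree.

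**What to change.** In 6.2.3 and 6.2.4, and before steps 15 and 18 of Appendix B, add wording such as: *If you have scored any GI symptom 10, do not take the next serving. Seek treatment as advised in section 9.2 and notify the study team. Continue the remaining assessments only if you are willing and able.* State whether the hold is final; the simplest rule is that it is. A lower trigger, for example somewhere in the 5 to 9 band that 7.3.1 calls severe, is the sponsor's clinical choice. If the portal already shows such a prompt, copy its wording into these sections.

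Report BHB by number of servings taken, using the consumption records in 5.5.2, so that partial exposure is not mixed with full exposure.

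The cost is a few lines of text, matching portal wording if absent, and a stated way to reach the study team. The participant applies the hold, so it does not wait on a staff response. No visits or samples are added. The downside is that a few participants may receive 11.5 g or 23.0 g instead of 34.5 g.
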